3.5.4.2 Dose Reduction

Per Investigator discretion, on a per-patient basis, dose may be reduced by half, ie, from 2 tablets daily to 1 tablet daily (in the morning). Each patient's dose may only be reduced once and may not be increased after reduction. Investigators should notify the Medical Monitor of all decisions to dose reduce on a per-patient basis.

3.5.5 Treatment Compliance

The appropriate amount of study drug will be dispensed to patients in prelabeled bottles at the Randomization, Week 1, Week 4, and Week 8 Visits. Patients will be asked to return all bottles

(including unused tablets) at the Week 1, Week 4, Week 8, and End of Treatment Visits for assessment of compliance with the dosing regimen.

Treatment compliance will be based on count of pills.

3.5.6 Blinding

This study is double blind and placebo controlled. The investigational product and placebo will be identical oral tablets.

Unblinding of a patient's treatment assignment is restricted to emergency situations and should only be used under circumstances where knowledge of the treatment is necessary for the proper handling of the patient. Except in a medical emergency, the Investigator and study center staff will remain blinded during the conduct of the study and until, at a minimum, all discrepancies in the clinical database are resolved (ie, at the time of the database lock). Individual patient treatment assignment unblinding is available to the Investigator through the interactive web response system (IWRS) in the event of an emergency. The Investigator should make all reasonable efforts to notify and discuss the circumstances requiring unblinding with the Medical Monitor or designee in advance of breaking the blind. If the treatment blind is broken, the reason and the date should be recorded and signed by the Investigator and information regarding the unblinding should be submitted as soon as possible to the Sponsor. If the Investigator is unblinded to the treatment assignment of a patient, the patient will be immediately withdrawn from study drug dosing and should follow early termination procedures (Section [3.4.3](#)).

The Sponsor may also break the blind in circumstances where unblinding is necessary for the safety of the patients.

To allow ongoing safety monitoring during the conduct of the study, members of an external DMC will review summaries of AE data by treatment groups randomly masked as A, B, and C and may request unblinded safety data. Please refer to Section [5.13](#) for more details.

3.5.7 Prior and Concomitant Therapy

At the Screening Visit, the following information will be recorded for each patient:

- All medications the patient is taking (ongoing)
- All prior medications taken during the 30 days before the Screening Visit

Beginning at the Screening Visit, any medication or change in medication taken by a patient during the study will be documented in the source documents and the eCRF along with the start and stop date and the reason for use.

Patients will be on a stable regimen of at least 1 antihyperglycemic medication and an ACEi or an ARB (see [Inclusion Criteria](#) for details), which may be modified during the study if medically necessary. Patients may be on a stable regimen of medication(s) for hypertension, which may be modified during the study if medically necessary. Permitted concomitant medications should be taken at the same time each day and may be taken at the same time as study drug.

Pharmacological stimulation of sGC by IW-1973 produces an increase in cGMP production. Concomitant administration of IW-1973 with an angiotensin receptor neprilysin inhibitor (ie, sacubitril/valsartan) should be allowed with caution as neprilysin inhibition results in increased cGMP concentrations via protection of natriuretic peptides.

Prohibited medications and supplements are listed in Sections [3.6](#) and [Appendix 1](#).

3.6 RESTRICTIONS

3.6.1 Prohibited Medicines and Supplements

Specific inhibitors of phosphodiesterase 5 (PDE5) (including sildenafil and tadalafil), nonspecific inhibitors of PDE5 (including dipyridamole and theophylline), any supplements for the treatment of erectile dysfunction, riociguat, and nitrates or NO donors in any form are prohibited from 7 days before the Randomization Visit on Day 1 through the duration of the trial.

Strong inhibitors of CYP3A are prohibited from 14 days before Randomization through the duration of the trial. Examples include azole antifungals, macrolide antibiotics, protease inhibitors, diltiazem, and concentrated grapefruit supplements.

See [Appendix 1](#) for a more detailed list of prohibited medicines and supplements.

3.6.2 Fluid and Food Restrictions

Patients should fast overnight (at least 8 hours) before predose blood and urine sample collections at all study visits, except for the Screening Visit.

Excessive grapefruit intake is prohibited from 14 days before Randomization through the duration of the trial.

Patient must agree not to make any major changes to their diet from the Screening Period through the Follow-up Visit.

3.6.3 Patient Activity

Patient must agree not to make any major changes to their exercise routine from the Screening Period through the Follow-up Visit.

3.6.3.1 Sexual Activity and Birth Control

Female patients who are not postmenopausal for at least 1 year (ie, 12 months of spontaneous amenorrhea [not induced by a medical condition or medical therapy]) or are not surgically sterile (ie, bilateral oophorectomy, hysterectomy, or tubal sterilization [tie, clip, band, or burn]) must agree to completely abstain from heterosexual intercourse or, if heterosexually active, must agree to use 1 of the following methods of birth control from the date she signs the ICF until 60 days after the final dose of study drug:

- Progesterone implant or an intrauterine device (IUD)
- Combination of 2 highly effective birth control methods (eg, diaphragm with spermicide plus a condom, condom with spermicide plus a diaphragm or cervical cap, hormonal contraceptive [eg, oral and transdermal patch] plus a barrier method, partner with vasectomy [conducted \geq 60 days before the Screening Visit or confirmed via sperm analysis] plus a hormone/barrier method).

Female patients must wait at least 60 days after the final dose of study drug to try to become pregnant and/or to undergo egg donation or egg harvesting for current or future in vitro fertilization.

Male patients who are not surgically sterile by vasectomy (conducted \geq 60 days before the Screening Visit or confirmed via sperm analysis) must agree to completely abstain from heterosexual intercourse or, if heterosexually active, must agree to use a combination of 2 highly effective birth control methods (eg, condom with spermicide plus partner IUD, condom with spermicide plus a partner diaphragm/cervical cap, partner use of hormonal contraceptive [including progesterone implant] plus a barrier method, or postmenopausal partner [for \geq 1 year] plus barrier method) from the Screening Visit through 60 days after the final dose of study drug.

Male patients must refrain from sperm donation during the study through at least 60 days after the final dose of study drug.

3.7 INDIVIDUAL STOPPING CRITERIA AND DMC REVIEWS

If any events included in [Table 3](#) are reported during the study and are judged to be both study drug related and an SAE (per causality and SAE definitions in Section [3.8.9.3](#)), individual stopping criteria or DMC review will be triggered per the criteria in Sections [3.7.1](#) and [Table 3](#), respectively. The inclusion of these AEs is based on the clinical experience with IW-1973, the prescribing information for riociguat, and the patient population for this study.

Table 3. Categories of SAEs Triggering Individual Stopping Criteria and Safety Committee Review

Treatment-emergent Study Drug-related SAE Category	# of patients to trigger DMC review
Renal failure (eGFR <15 mL/min/1.73 m ² ; dialysis or renal transplant indicated)	2
Spontaneous bleeding events (eg, hemoptysis, subarachnoid or subdural hemorrhage, hematemesis, hematochezia)	2
Symptomatic hypotension-related events (eg, syncope)	2

DMC=Data Monitoring Committee; eGFR=estimated glomerular filtration rate; SAE=serious adverse event

3.7.1 Individual Stopping Criteria

On an individual basis, a patient will be discontinued from study drug dosing if 1 SAE from [Table 3](#) is reported. At the Investigator's or Sponsor's discretion, any AE(s) of concern can likewise be the basis for patient discontinuation from the trial.

3.7.2 Data Monitoring Committee Reviews

An independent DMC comprising experts in cardiovascular and/or renal disease and/or diabetes and a biostatistician will review trial safety data both periodically and if SAEs from the same category in [Table 3](#) are reported at the incidence indicated in the table (eg, 2 patients with spontaneous bleeding SAEs). After review of safety data, the DMC will recommend trial continuation, continuation with modification, or termination. Refer to [Section 5.13](#) for details regarding the DMC, the scheduled and ad hoc reviews, the data that will be provided for review, and Sponsor decision-making.

3.8 STUDY PROCEDURES AND ASSESSMENTS

3.8.1 Informed Consent

Informed consent procedures will comply with the Code of Federal Regulations (CFR) 21, Parts 50 and 312.

The written ICF must be approved by the Institutional Review Board (IRB) for the purposes of obtaining and documenting consent.

Before entry into the study, each patient will be provided with a written explanation of the study. It is the responsibility of the Investigator or appropriately trained health professional to give each patient full and adequate information regarding the objectives and procedures of the study and the possible risks involved. Patients will then be given the opportunity to ask questions and the Investigator will be available to answer questions as needed. Patients will be informed of their right to withdraw from the study at any time without prejudice. After this explanation and before entering the study, the patient will voluntarily sign the study-specific ICF. The patient will receive a copy of the signed and dated ICF. The Investigator must retain each patient's original signed ICF.

If new information becomes available that may be relevant to the patient's consent and willingness to participate in the study, the ICF will be revised. The revised ICF must be submitted to the IRB for review and approval before its use.

3.8.2 Medical History

A complete medical history, including history of smoking, will be recorded at the Screening Visit.

3.8.3 [REDACTED]

3.8.4 Physical Examination

A complete physical examination will be performed according to the [Schedule of Events](#). The physical examination of each patient should include examination and assessment of the following:

General appearance	Head, eyes, ears, nose, and throat
Cardiovascular system	Neck
Respiratory system	Musculoskeletal system
Abdomen/liver/spleen	Nervous system
Lymph nodes	Skin
Neurologic status	Mental status

Breast, genitourinary, and rectal examinations are optional and may be performed at the discretion of the Investigator. Any new, clinically significant abnormal findings from the physical examination will be reported as an AE.

Each patient's weight will be recorded at each study visit; height will only be recorded at the Screening Visit.

3.8.5 Respiratory Rate and Temperature

Respiratory rate and oral temperature (°C) will be measured according to the [Schedule of Events](#) and documented on the eCRF. Respiratory rate should be measured after the patient has been seated for at least 5 minutes.

3.8.6 Hemodynamics

Hemodynamic assessments will include seated BP and pulse, orthostatic (seated-to-standing) BP and pulse, and ABPM. Outside of the ABPM assessments, all other BP and pulse measurements will be taken by automated office blood pressure (AOBP); manual measurements are allowed in cases in which an AOBP machine malfunctions or is not available.

Blood pressure and pulse measurements at the Screening and Baseline Visits will be performed with patients in the seated position. Seated BPs for study eligibility will be the average of 3 measurements obtained at 2-minute intervals after the patient has been sitting quietly for at least 5 minutes.

Blood pressure and pulse measurements at the Randomization, Week 4, Week 8, End of Treatment, and Follow-up Visits will be seated-to-standing for calculation of orthostatic BP and pulse. Patients should sit quietly for at least 5 minutes before seated measurements are taken, and then assume a standing position for 30 to 60 seconds before standing measurements are taken. At the End of Treatment visit, seated predose BP will be the average of 3 measurements.

When applicable, BP and pulse measurements should be taken before blood draws. All predose BP and pulse measurements should be taken before all oral and any antihypertensive concomitant medications.

Patients will begin 24-hour ABPM at the study site during the Baseline and End of Treatment Visits and will begin 12-hour ABPM at the study site during the Week 4 and Week 8 Visits. Patients will return the ABPM equipment to the study site at the following study visit.

Baseline Visit ABPM assessment: At least 65% compliance is preferred, with no more than 10 missed readings during the day (7 am – 10 pm) and/or 3 missed readings at night (10:30 pm – 6:30 am), and no more than 6 missed readings in succession. (If a patient's ABPM assessment does not meet these criteria, the medical monitor must be contacted PRIOR to randomizing the patient.)

At the Week 4, Week 8, and End of Treatment Visits, ABPM should begin before study drug administration.

3.8.7 Electrocardiograms

A 12-lead electrocardiogram (ECG) will be performed according to the [Schedule of Events](#) and documented on the eCRF. Electrocardiograms should be obtained after the patient has been supine for at least 5 minutes. At the Screening and Baseline Visits, if on initial ECG, QTcF is ≥ 450 msec for male patients or is ≥ 470 msec for female patients, the ECG will be repeated 2 more times, and the average of the 3 QTcF values will be used to determine eligibility.

3.8.8 Clinical Laboratory Tests

Blood and urine samples for clinical laboratory tests will be collected according to the [Schedule of Events](#). Except for the Screening Visit, patients should fast for at least 8 hours before sample collections.

The clinical laboratory evaluations will include the serum chemistry, hematology (complete blood count [CBC]), coagulation, UA, and additional tests as presented in [Table 4](#).

Table 4. Clinical Laboratory Tests

Serum Chemistry	Hematology (CBC)	Urinalysis
Albumin	Hematocrit	Color and appearance
Alkaline Phosphatase	Hemoglobin	pH and Specific Gravity
ALT	Platelet count	Bilirubin
AST	MPV	Glucose
Bicarbonate	RBC count	Ketones
BUN	WBC count	Leukocytes
Calcium	WBC differential	Nitrites
Chloride	(% & absolute):	Occult blood
Cholesterol	Basophils	Protein
Creatinine	Eosinophils	Urobilinogen
GGT	Lymphocytes	Microscopic
Glucose	Monocytes	Including bacteria, RBCs, WBCs per HPF if dipstick is abnormal
HDL-c	Neutrophils	
LDH	RBC indices	
LDL-c (calculated)	MCH	Additional blood tests
Magnesium	MCHC	Hemoglobin A1c
Phosphorus	MCV	Fasting plasma glucose
Potassium	RDW	Fasting plasma insulin
Sodium		
Total Bilirubin	Coagulation	Additional urine tests
Total Protein	aPTT	Urine albumin & creatinine for UACR*
Triglycerides	Prothrombin time	Urine cotinine
Uric acid	INR	

ALT=alanine aminotransferase; aPTT=activated partial thromboplastin time; AST=aspartate aminotransferase; BUN=blood urea nitrogen; CBC=complete blood count; GGT=gamma glutamyl transferase; HPF=high power field; INR=International Normalized Ratio; LDH=lactate dehydrogenase; MCH=mean corpuscular hemoglobin; MCHC=mean corpuscular hemoglobin concentration; MCV=mean corpuscular volume; MPV=mean platelet volume; RBC=red blood cell; RDW=red blood cell distribution width; UACR=urine albumin-creatinine ratio; WBC=white blood cell.

* At the Screening Visit, a single urine sample, which may not be first void, may be collected. Thereafter, samples should be 2 first-void urine samples collected on the 2 consecutive mornings before each scheduled study visit. Patients will be supplied with specimen collection supplies at the preceding study visit.

3.8.8.1 Pregnancy Tests

For female patients, a negative pregnancy test (by urine dipstick) must be documented at all study visits with results available before dosing, where applicable. In the event of a positive pregnancy test, the test will be repeated. If pregnancy is confirmed, see Section [3.8.9.5](#). Female patients who are postmenopausal (no menses for ≥ 12 consecutive months) or surgically sterile (ie, bilateral oophorectomy, hysterectomy, or tubal sterilization [tie, clip, band, or burn]) do not have to have a urine pregnancy test.

3.8.8.2 Hepatitis, HIV, and Drug Screens

Screens for a hepatitis panel (including HBsAg and anti-HCV) and human immunodeficiency virus (HIV) antibody will be performed at the Screening Visit.

A urine drug screen for the following drugs of abuse will be performed at the Screening Visit:

Amphetamines	Cocaine	Phencyclidine (PCP)
Barbiturates	Marijuana	Propoxyphene
Benzodiazepines	Opiates	

3.8.8.3 Urine Albumin Creatinine Ratio (UACR)

UACR will be calculated as urine albumin (mg/dL) / urine creatinine (g/dL).

Urine albumin and urine creatinine levels will be determined as part of the clinical laboratory tests ([Table 4](#)). At the Screening Visit, a single urine sample, which may not be first void, will be collected for determination of albumin and creatinine levels. For subsequent study visits, patients will be given urine collection supplies and will collect 2 first-void urine samples on the 2 consecutive mornings before each scheduled visit.

3.8.8.4 Estimated Glomerular Filtration Rate (eGFR)

Estimated glomerular filtration rate will be based on the serum creatinine level determined as part of the clinical laboratory tests ([Table 4](#)) and will be calculated according to the Chronic Kidney Disease Epidemiology Collaboration (CKD-EPI) creatinine equation.[\(1\)](#)

The CKD-EPI equation, expressed as a single equation, is

$$\text{GFR} = 141 \times \min(\text{Scr}/\kappa, 1)^\alpha \times \max(\text{Scr}/\kappa, 1)^{-1.209} \times 0.993^{\text{Age}} \times 1.018 \text{ [if female]} - 1.159 \text{ [if black]},$$

where Scr is serum creatinine, κ is 0.7 for females and 0.9 for males, α is -0.329 for females and -0.411 for males, min indicates the minimum of Scr/k or 1, and max indicates the maximum of Scr/k or 1.

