Clinical Laboratory Assessments

Complete blood count, serum chemistry panel, urinalysis, coagulation panel, UACR (urine albumin [mg/dL] / urine creatinine [g/dL]), estimated glomerular filtration rate (eGFR; by the Chronic Kidney Disease Epidemiology Collaboration [CKD-EPI] creatinine equation), hemoglobin A1c, Homeostatic Model Assessment to estimate insulin resistance (HOMA-IR), [REDACTED], urine pregnancy, and screens for hepatitis, human immunodeficiency virus, and drugs of abuse.

Hemodynamics and Vital Signs

Seated and standing BP (systolic and diastolic) and pulse measurements by automated office blood pressure (AOBP), ambulatory BP (systolic and diastolic) and pulse monitoring, respiratory rate, oral temperature. Orthostatic (standing minus seated) measurements will be calculated for BPs and pulse.

[REDACTED]

[REDACTED]

Other

Adverse-event recording, electrocardiograms (ECGs), physical examinations, concomitant medications.

Pharmacokinetics

Plasma IW-1973 concentrations will be measured.

[REDACTED]

[REDACTED]

[REDACTED]

[REDACTED]

[REDACTED]

[REDACTED]

[REDACTED]

[REDACTED]

Study Endpoints

Primary Endpoints

- Primary Safety: Incidence of TEAEs and study drug-related TEAEs
- Primary Efficacy: Change from baseline in UACR over Weeks 8 and 12

Statistical Methods

Sample Size Determination

Using an estimate of standard deviation of 0.67, a sample size of 40 patients per treatment group would provide approximately 80% power to detect a mean between-group difference of -0.376 units in change from baseline in log-transformed UACR over 12 weeks, with a one-sided significance level of 0.05 for at least 1 dose versus placebo comparison. This difference corresponds to a 31% between-group reduction of geometric mean change from baseline in UACR. Assuming a drop-out rate of 20%, approximately 150 patients will be randomly assigned in a 1:1:1 ratio (approximately 50 patients per treatment group) to 20 mg IW-1973, 40 mg IW-1973, or placebo.

Analysis Populations

Safety Population: The Safety Population will consist of all randomized patients who receive at least 1 dose of study drug. Patients in this population will be evaluated according to the treatment they actually received.

Intent-to-Treat (ITT) Population: The ITT Population will consist of all randomized patients who receive at least 1 dose of study drug. Patients in this population will be evaluated according to the treatment group they were assigned at Randomization.

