3. Patient has type 2 diabetes diagnosed by a physician or nurse practitioner ≥ 6 months before the Screening Visit, has been on ≥ 1 antihyperglycemic medication for ≥ 12 weeks preceding the Randomization Visit, and has been on a stable regimen (ie, same drug and same dose) of ≥ 1 antihyperglycemic medication for ≥ 28 days preceding the Randomization Visit.
(Modification of short-acting insulin throughout the Screening Period will not affect eligibility.)
4. Patient has been on a stable regimen (ie, same drug and dose) of an angiotensin-converting enzyme inhibitor (ACEi) or an angiotensin receptor blocker (ARB), for ≥ 28 days preceding the Randomization Visit and is expected to remain on their regimen through the Follow-up Visit. (Note: These medications may be modified during the study if medically necessary.)
5. If patient is on medications for hypertension, regimen (drug[s] and dose[s]) must be stable for ≥ 28 days preceding the Randomization Visit and is expected to remain stable through the Follow-up Visit. (Note: Medications for antihypertension may be modified during the study if medically necessary.)
6. Patient has the following:
 - a. Estimated glomerular filtration rate (eGFR) 30 to 75 mL/min/1.73 m² by the Chronic Kidney Disease Epidemiology Collaboration (CKD-EPI) creatinine equation (1) at the Screening and Baseline Visits
 - b. Urine albumin creatinine ratio (UACR) >200 mg/g and <5000 mg/g at the Screening and Baseline Visits (at the Baseline Visit, the mean of the 2 first morning void tests will be used to determine eligibility)
 - c. Serum albumin >3.0 g/dL at the Screening and Baseline Visits
 - d. Hemoglobin A1c (HbA1c) $\leq 12\%$ at the Screening and Baseline Visits
 - e. Systolic blood pressure (BP) of 110 to 160 mm Hg based on the average of 3 seated automated office blood pressure (AOBP) measurements at the Screening and Baseline Visits
7. Female patient must be postmenopausal (no menses for ≥ 12 consecutive months); surgically sterile (ie, bilateral oophorectomy, hysterectomy, or tubal sterilization [tie, clip, band, or burn]); must agree to completely abstain from heterosexual intercourse; or, if heterosexually

active, must agree to use 1 of the following methods of birth control from the date she signs the ICF until 60 days after the final dose of study drug:

- a. Progesterone implant or an intrauterine device (IUD)

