3.5.2 Method of Assigning Patients to Treatment Groups

Approximately 150 patients who meet all of the inclusion criteria and none of the exclusion criteria will be stratified by Baseline eGFR (ie, eGFR 30 to 45, >45 to 60, and >60 to 75 mL/min/1.73 m²) and randomized 1:1:1 to 20 mg IW-1973, 40 mg IW-1973, or placebo at the Randomization Visit on Day 1.

Patients will be randomized through central randomization. The computer-generated randomization schedule will be prepared by an independent statistician not otherwise associated with the study.

Patients and Investigators will be blinded to treatment assignments in this study (see Section 3.5.6 for more details on blinding in this study).

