5.9 EFFICACY ANALYSES

All efficacy analyses will be based on the ITT and PP Populations.

Corresponding with the primary efficacy objective of the trial, the primary inference for hypothesis testing is the treatment difference between the placebo group and the IW-1973 groups on the change from baseline in log UACR over Weeks 8 and 12. The primary efficacy analysis will be conducted using the ITT population using a mixed-effects model repeated measures (MMRM) analysis with change from baseline in log-transformed UACR as the response variable, treatment, site, visit, treatment-by-visit interaction, and baseline eGFR stratum as fixed effects, and baseline log UACR and baseline MAP as covariates with unstructured as the variance-covariance structure. Treatment differences between the pooled IW-1973 dose groups and the placebo group will be estimated overall. The null hypothesis of the test will be interpreted as equality between the placebo and pooled treatment groups, and rejection of the null hypothesis as evidence that the pooled IW-1973 groups have a greater effect on lowering UACR than the placebo group. If the null hypothesis is rejected, the nature of these differences

will be explored further by estimating the treatment differences between each IW-1973 dose group and the placebo group overall and at each assessment timepoint. Least square (LS) means, and LS mean differences between each IW-1973 group and placebo, and their associated one-sided 95% confidence intervals will be calculated overall and for each assessment timepoint. The contrasts between each IW-1973 dose group and the placebo group at each assessment timepoint will be compared using a one-sided significance level of 0.05. If the treatment-by-visit interaction is significant at the 0.1 significance level, LS mean treatment differences relative to the previous visit will also be presented.

All change-from-baseline efficacy parameters will use the same MMRM model.

Treatment group differences in the proportion of patients who achieved a 30% or 40% reduction in UACR from baseline to Week 12 will be analyzed using Cochran-Mantel-Haenszel (CMH) test stratified by baseline eGFR stratum.

Summary statistics will be presented by treatment group for the biomarker parameters. Change from baseline in these variables will also be presented, where applicable.

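### The eGFR equation in Section 3.8.8.4 subtracts 1.159 for Black patients where every other term multiplies: very likely a sign error, harmful only if the printed line was programmed

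*Protocol*

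**What the plan says.** Section 3.8.8.4 states that eGFR will be "calculated according to the Chronic Kidney Disease Epidemiology Collaboration (CKD-EPI) creatinine equation", with a literature citation. It then introduces a formula with the words "The CKD-EPI equation, expressed as a single equation, is". The formula runs: 141, times a minimum term, times a maximum term, times 0.993 to the power of age, times 1.018 for women. The race term follows with a minus sign: "if female]} - 1.159".

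This is the only place in the protocol where the equation is written out. The Synopsis (Clinical Laboratory Assessments), inclusion criterion 6a and Section 3.4.1 name the equation without restating it.

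The result is used in these places:

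- Criterion 6a requires 30 to 75 mL/min/1.73 m², "by the Chronic Kidney Disease Epidemiology Collaboration (CKD-EPI) creatinine equation (1) at the Screening and Baseline Visits".
- Section 3.5.2: patients "will be stratified by Baseline eGFR" in three bands, 30 to 45, >45 to 60 and >60 to 75.
- Section 5.9: the MMRM includes "baseline eGFR stratum as fixed effects", and the CMH test for UACR responders is stratified the same way.
- Table 3 (Section 3.7) uses eGFR below 15 in the renal failure category.

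**The concern.** The sex and race terms are built alike: a constant close to 1 followed by a condition in brackets. A constant of that kind makes sense as a factor. As a factor, 1.159 raises eGFR by 15.9%. As a subtraction it lowers eGFR by a flat 1.159 mL/min/1.73 m², whatever the kidney function. Both the direction and the size of the adjustment change, and the printed line does not share the form of the rest of the equation.

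Because Section 3.8.8.4 is the only written version, it is the line a programmer would copy. If that happened at the laboratory, in the randomisation system or in the analysis code, Black patients would get an eGFR that is too low. Some near the lower limit of 30 would be turned away, some above the upper limit of 75 would be let in, and others would be placed in a lower stratum. The error would be confined to one patient group and would not be obvious from a baseline table.

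**Working it through.** The protocol gives no worked eGFR value, so there is no figure of its own to reproduce. The check compares the printed line with the same line using 1.159 as a factor.

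**Inputs (Section 3.8.8.4).** Constants 141, −1.209, 0.993, 1.018 and 1.159; κ = 0.7 (women) or 0.9 (men); α = −0.329 or −0.411. Cut-points 30, 45, 60, 75 (criterion 6a, Section 3.5.2) and 15 (Table 3).

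**Step 1: the gap between the two forms.** Let b be the equation before the race term.

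- As printed: b − 1.159
- As a factor: 1.159 × b
- Gap: 0.159 × b + 1.159

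A printed value c means b = c + 1.159, so the factor form gives 1.159 × (c + 1.159). For c = 30 this is 1.159 × 31.159 = 36.1.

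| Printed eGFR | eGFR with 1.159 as a factor | Gap |
|---|---|---|
| 15 | 18.7 | 3.7 |
| 30 | 36.1 | 6.1 |
| 45 | 53.5 | 8.5 |
| 60 | 70.9 | 10.9 |
| 75 | 88.3 | 13.3 |

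**Step 2: what this means in creatinine.** Section 3.8.8.4 gives no unit for creatinine; mg/dL is assumed here. The illustration is a Black patient aged 60. All creatinine values below exceed κ, so the minimum term equals 1 and

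Scr = κ × (b / C)^(−1/1.209), where C = 141 × 0.993^60 = 92.51 for men, and 92.51 × 1.018 = 94.17 for women.

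For a target eGFR e, b = e + 1.159 as printed and b = e / 1.159 as a factor.

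| eGFR | Men, printed | Men, factor | Women, printed | Women, factor |
|---|---|---|---|---|
| 75 | 1.06 | 1.21 | 0.83 | 0.96 |
| 60 | 1.27 | 1.46 | 1.00 | 1.15 |
| 45 | 1.60 | 1.85 | 1.26 | 1.46 |
| 30 | 2.21 | 2.58 | 1.75 | 2.04 |

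If the factor form is correct, then for men aged 60 the printed line:

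- admits creatinine of about 1.06 to 1.21, which should be above the upper eGFR limit;
- excludes about 2.21 to 2.58, which should be eligible;
- puts about 1.27 to 1.46 in the >45 to 60 stratum instead of >60 to 75;
- puts about 1.60 to 1.85 in the 30 to 45 stratum instead of >45 to 60.

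**Step 3: three single patients, all aged 60.**

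| Patient | b | Printed | Factor | Consequence |
|---|---|---|---|---|
| Woman, Scr 1.8 | 30.1 | 28.9 | 34.8 | ineligible versus eligible |
| Man, Scr 1.2 | 65.3 | 64.2 | 75.7 | eligible versus ineligible |
| Woman, Scr 1.3 | 44.6 | 43.4 | 51.6 | stratum 30 to 45 versus >45 to 60 |

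For patients to whom the race term does not apply, the two forms are identical.

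**The case against.** The case against rests on four points.

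1. **One machine-read symbol.** The evidence is a single operator in a transcribed formula. Signs are fragile elsewhere too: the Synopsis puts the Baseline Visit at Day 7, while Section 3.9.1.2 has Day −7. This stands as a reason to look at the original page first. Against it, all the other multiplication signs in the same formula were read correctly.

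2. **The correct operator cannot be proved from the protocol.** The equation is printed once and the cited paper is not at hand. This also stands. The parallel with the sex term makes a factor very likely, not certain. The inconsistency of form is visible without the source.

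3. **The named equation governs.** The section tells the reader to use the cited equation, and the printed line only claims to restate it. Nothing in the protocol suggests that any system was built from that line. This is right, and it is why the harm is conditional.

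4. **The treatment comparison is barely touched even in the worst case.** UACR is calculated from urine albumin and creatinine, not from eGFR. The stratum is fixed before randomisation and any misplacement applies to all arms alike. The sample size does not use the formula. In the below-15 category the printed line would flag more cases, not fewer. All of this stands, and it keeps the point well short of a threat to the primary result.

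None of these points explains why one term in a product should be subtracted, and no other part of the protocol corrects it.

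**Conclusion.** The concern holds. The only written form of the eGFR equation in the protocol is inconsistent with itself, and the minus before 1.159 is very likely an error for a multiplication sign. If the printed line was programmed, Black patients at printed values of 30 to 75 would have an eGFR 6.1 to 13.3 mL/min/1.73 m² too low, which is about 40% to 90% of a 15-unit stratum (6.1/15 = 0.41; 13.3/15 = 0.89). That would misjudge criterion 6a and the stratum for some of them. If the cited equation was used, no patient is affected.

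This rests on three assumptions: that the minus is in the original page and is not a reading fault; that the cited equation multiplies; and, for the creatinine figures only, that creatinine is in mg/dL. The protocol does not give the expected share of Black patients, so the effect on the trial as a whole cannot be sized. The line should be corrected because it sits under eligibility and stratification, but it does not undermine the primary efficacy analysis.

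**What to change.** 1. Check the operator before 1.159 on the original page and against the cited equation. If confirmed, replace the minus with a multiplication sign.
2. Obtain confirmation that the laboratory, the randomisation system and the analysis programs use the cited multiplicative equation.
3. Only if the printed form was ever programmed: keep the strata as randomised in the primary model and report a sensitivity analysis with strata recalculated from corrected eGFR.

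The first two steps cost a one-symbol correction and a query to the laboratory and the randomisation vendor. The third costs one additional analysis.
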